A Phase I Randomized Controlled Trial of Intratumoral Lidocaine Injection Before Transoral Robotic Surgery (TORS) and Neck Dissection for HPV-Associated Oropharyngeal Squamous Cell Carcinoma

Regulatory Sponsor: [name]
University of Pennsylvania
Department of Otorhinolaryngology – Head & Neck Surgery
[name]
[name]
[name]
[contact]
[contact]

Sub-Investigators: Radiation Oncology: [name]
Otorhinolaryngology: [name]
Otorhinolaryngology: [name]
Otorhinolaryngology: [name], PhD
Otorhinolaryngology: [name]
Pathology: [name], PhD

Biostatistics: [name], MS

Protocol Number: 856397

UPCC Number: 12324

CONFIDENTIAL

This document is confidential and the property of the University of Pennsylvania. No part of it may be transmitted, reproduced, published, or used by other persons without prior written authorization from the study sponsor.

Table of Contents

STUDY SUMMARY	3
1 INTRODUCTION	6
2 STUDY OBJECTIVES	9
3 STUDY DESIGN	9
4 SUBJECT SELECTION AND WITHDRAWAL.....	10
5 STUDY PROCEDURES	13
6 STATISTICAL PLAN	16
7 SAFETY AND ADVERSE EVENTS.....	17
8 DATA HANDLING AND RECORD KEEPING	21
9 DATA AND SAFETY MONITORING PLAN.....	22
10 ETHICAL CONSIDERATIONS	23
11 STUDY FINANCES	24
12 PUBLICATION PLAN	25
13 REFERENCES	25

List of Abbreviations

[figure not shown]
Oropharyngeal squamous cell carcinoma	OPSCC
Human papillomavirus	HPV
Transoral Robotic Surgery	TORS
Chemoradiotherapy	CRT
Intensity-modulated radiation therapy	IMRT
Perineural invasion	PNI
Extranodal extension	ENE
Quality of Life	QOL
Bitter taste receptor	T2Rs
Voltage gated sodium channel	VGSC
Pathologic tumor response	pTR

Study Summary

Title	A Phase I Randomized Controlled Trial of Intratumoral Lidocaine Injection Before Transoral Robotic Surgery (TORS) and Neck Dissection for HPV-Associated Oropharyngeal Squamous Cell Carcinoma
Short Title	Intratumoral Lidocaine Injection Before Oropharyngeal Cancer Surgery
Protocol Number	
Phase	Phase I
Study Duration	2-years
Study Center(s)	Single-center
Objectives	
Primary: To determine if intratumoral lidocaine injection prior to TORS and neck dissection for HPV associated OPSCC is 1) safe and 2) causes a major pathologic treatment effect.
 
Secondary: To determine if intratumoral lidocaine injection prior to TORS and neck dissection for HPV associated OPSCC improves the locoregional control rates, progression-free survival, metastasis-free survival, and overall survival.

Number of Subjects	30 evaluable subjects
Diagnosis and Main Inclusion Criteria	
 - ≥18 years old with OPSCC undergoing direct laryngoscopy for consideration of TORS and neck dissection.
Study Regimen	
 - Patients will be randomized and blinded to intratumoral injection of 1% lidocaine (intervention arm) or no injection (control arm) at the time of direct laryngoscopy and biopsy prior to TORS and neck dissection. 
 o Intervention arm: While under general anesthesia after direct laryngoscopy with biopsy, 1% lidocaine will be injected under direct visualization (not exceeding the maximum tolerated dose of 4.5 mg/kg body weight) into the primary tumor with the aim to distribute the lidocaine evenly into the tumor. o Control arm: Direct laryngoscopy with biopsy with no injection. - Blood samples will be obtained before and after direct laryngoscopy/study intervention. - Pathologic tumor response (pTR) will be determined from surgical specimens.

Statistical Methodology	
This is a patient-blinded, randomized phase I study assessing safety, pathologic treatment effects, and oncologic outcomes from intratumoral lidocaine injection vs no injection at the time of direct laryngoscopy prior to TORS and neck dissection for HPV associated OPSCC. The total sample size is estimated to be 30 patients total (split approximately equally between the two groups). The proportion of patients with a pathologic tumor response (pTR) $\geq 50\%$ (pTR-2) in the primary tumor following surgical resection will be compared between intervention and control arms using a one-sided Fisher's exact test with a significance level of 0.05. The 2-year locoregional control (LRC) rates, progression-free survival (PFS), metastasis-free survival (MFS), and overall survival (OS) will be estimated using the Kaplan–Meier method and compared using log-rank test between the two arms.

-------------------------	-------------------------------------------------------------------------------------------------------------------------------------------------------------------------------------------------------------------------------------------------------------------------------------------------------------------------------------------------------------------------------------------------------------------------------------------------------------------------------------------------------------------------------------------------------------------------------------------------------------------------------------------------------------------------------------------------------------------------------------------------------------------------------------------------------------------------------------------------------------------------------------------------------------------------------------------

Study Schema

Primary endpoints: 1) safety, 2) proportion of patients with pTR-2

Secondary endpoints: 2-year LRC, MFS, PFS, OS

* Denotes trial-related (i.e., not institutional standard of care)

1 Introduction

Based on evidence that lidocaine may activate apoptosis in cancer cells and/or limit metastasis, this randomized phase I study will establish the safety and efficacy of intratumoral lidocaine injection at the time of direct laryngoscopy prior to TransOral Robotic Surgery (TORS) and neck dissection for oropharyngeal squamous cell carcinoma (OPSCC). The primary objective of the study is to determine if intratumoral lidocaine injection is safe and causes a major pathologic treatment effect in the primary tumor following surgical resection. The secondary objectives will be to determine if intratumoral lidocaine injection improves locoregional control (LRC) rates, progression-free survival (PFS), metastasis-free survival (MFS), and overall survival (OS) compared to no injection (standard of care).

Background

Oral squamous cell carcinomas, which are located in the oral cavity and pharynx, accounted for roughly 50,000 new cancer diagnoses in the US in 2020 with an anticipated increase to 76,000 by 2040.¹ The increase in incidence is predominantly attributed to the rise in human papillomavirus (HPV)-associated OPSCCs which now represent most OPSCC cases and typically occur in the tonsils or base of tongue.² Compared to HPV-negative OPSCCs, HPV associated OPSCCs tend to have relatively higher nodal burden at presentation and generally affect younger patients with higher performance status and fewer co-morbid conditions.^{3, 4} Treatment for OPSCCs is selected based on the clinical and pathologic features and typically includes either definitive chemoradiation or surgery (TORS and selective neck dissection) followed by adjuvant radiation (+/- chemotherapy).⁵⁻⁸ Candidacy for TORS is typically assessed with direct laryngoscopy (with biopsy when indicated) to help evaluate the tumor extent and relevant anatomy. Primary surgery or primary radiation for HPV associated OPSCC both allow for favorable disease control (>95% LRC rates) and OS (~90% 3-year OS);⁹⁻¹³ however, a subset of patients recur and are unable to be successfully salvaged.^{13, 14} Furthermore, the available treatments have associated toxicities including life-threatening sequelae or side-effects that impact quality of life (QoL) such as dysphagia, xerostomia, dysgeusia, neck fibrosis, and chronic pain.¹⁵⁻¹⁸ Several completed and ongoing de-escalation trials have sought to limit treatment-related morbidity by de-intensifying therapy for HPV associated OPSCC.¹⁹⁻²² However, there is a clear need for novel therapies with low side-effect profiles to improve disease outcomes while maintaining QoL.

Study Rationale, Preliminary Data, and Significance

Lidocaine, a commonly used local anesthetic, has potential relevance for OPSCC treatment through its activation of bitter taste receptors (T2Rs) and inhibition of voltage gated sodium channels (VGSCs). T2Rs are G-protein-coupled receptors (GPCRs) that bind bitter agonists and are best known for their gustatory role on the tongue²³. These receptors are also

expressed in other normal tissues throughout the body where they serve a diverse array of chemosensory and immune functions.²⁴⁻²⁹ More recently, T2Rs have been investigated in several cancers including GI,³⁰⁻³⁶ pancreatic,^{37, 38} breast,³⁹ thyroid,⁴⁰ acute myeloid leukemia,⁴¹ and head and neck squamous cell carcinoma including HPV associated OPSCCs.⁴² T2Rs in head and neck squamous cell carcinoma cells are activated by bitter compounds which trigger downstream Ca^{2+} responses, mitochondrial depolarization, caspase activation, and apoptosis.⁴² T2R expression levels have been shown to correlate with survival in head and neck squamous cell carcinomas⁴² and several other solid tumors including lung, prostate, and esophageal cancer.⁴³ Of the 25 T2R isoforms in humans, T2R14 is being studied most actively.^{24, 44, 45} Interestingly, the local anesthetic lidocaine is a bitter agonist for T2R14.⁴⁶ In head and neck squamous cell carcinoma, lidocaine decreases cancer viability, depolarizes the mitochondrial membrane potential, elevates mitochondrial reactive oxygen species, induces apoptosis, and can inhibit the proteasome in a T2R14-dependent manner.⁴⁷ Furthermore, analysis of The Cancer Genome Atlas (TCGA) data suggests that T2R14 expression is increased in HPV associated OPSCCs compared to HPV-negative OPSCCs.

In addition to the newly described T2R14-mediated effects and increased receptor expression in HPV associated OPSCCs,⁴⁷ lidocaine has been shown to also have beneficial effects in certain cancer types through its inhibitory effects on VGSCs.⁴⁸⁻⁵⁶ VGSCs have been shown to be expressed in human cancers including prostate⁵⁷, breast cancer,⁵⁸⁻⁶⁰ and head and neck squamous cell carcinoma.⁵⁴⁻⁵⁶ It has been suggested that VGSCs are involved in oncogenic processes and are associated with metastatic behavior.⁴⁸⁻⁵⁶ For example, sodium channel protein type 5 subunit alpha, also known as Nav1.5, is highly expressed in head and neck squamous cell carcinomas and associated with TNM stage, lymph node metastasis, and other clinical features. *In vitro* inhibition of Nav1.5 promotes apoptosis and decreases proliferation, migration, and invasion. Additionally, Nav1.5 is thought to potentially be involved in the progression of head and neck squamous cell carcinomas through the Wnt/β-catenin signaling pathway.⁵⁶ To our knowledge, there are no published studies evaluating oncologic outcomes for the *in vivo* clinical use of local anesthetics such as lidocaine in patients with OPSCC, though these drugs have been studied in other solid tumors including breast cancer.^{48, 52, 61, 62}

In vitro inhibition of VGSCs in breast cancer has been shown to reduce cell proliferation, motility, and invasion while encouraging focal adhesion, potentially reducing the metastatic capability of primary tumors.⁶⁰ Clinical studies in patients undergoing breast cancer tumor resection suggested possible improved outcomes with use of local anesthetic, specifically lidocaine, at the primary tumor site.⁶³⁻⁶⁵ These observations led to the design of a recently published randomized controlled trial in the *Journal of Clinical Oncology* assessing the effect of lidocaine infiltration around the primary breast tumor prior to surgical resection in women with early breast cancer. This multi-institutional trial of nearly 1600 patients

demonstrated significantly increased 5-year DFS (86.6% vs 82.6%) and OS (90.1% and 86.4%) in the peritumoral lidocaine injection group compared to the no injection group.⁶⁶

Surgery for solid tumors is known to modify gene expression and metastatic potential, cause dissemination of tumor cells, stimulate growth of micrometastasis, and inhibit the immune system.⁶⁷⁻⁷² Simple interventions before or during oncologic surgery that can improve outcomes and potentially reduce metastasis are appealing, especially when they are not particularly time-consuming or expensive. Injection of local anesthetic such as lidocaine (with or without vasoconstrictive agents like epinephrine) is already commonly used during head and neck surgery to reduce general anesthetic requirements and provide hemostasis.⁷³ Therefore, lidocaine injection into the primary tumor in OPSCC would likely be easy to implement at the time of direct laryngoscopy while a patient is already under general anesthesia. Given the potential oncologic benefits and limited side-effects, intratumoral lidocaine injection may be particularly beneficial in HPV associated OPSCC prior to definitive TORS and neck dissection.

Dosing Rationale

Subcutaneous injection of 1% lidocaine (40 mM) is frequently used for local anesthesia during surgical operations and minor procedures.⁷³ Concentrations of lidocaine lower than 1% or 40 mM (including 10 mM) were sufficient to decrease head and neck SCC viability and cell proliferation and induce apoptosis *in vitro*; this effect was reduced or lost at lower concentrations of 5 mM or 1 mM.⁴⁷ The previously referenced breast cancer randomized controlled trial demonstrated that 1% lidocaine injected around the primary tumor was associated with ~4% higher DFS and OS compared to no injection.⁶⁶ Therefore, the current study will use 1% lidocaine injected under direct visualization (not exceeding the maximum tolerated dose of 4.5 mg/kg body weight) into the primary tumor with the aim to distribute the lidocaine evenly into the tumor. The maximum tolerated dose of 1% lidocaine (4.5 mg/kg body weight) is ~31.5 mL total for a 70 kg person.

Most tumors are stage T1 or T2 with greatest dimension 2 or 4 cm, respectively. A spherical tumor with diameter of 2 cm corresponds to a volume of 4.2 mL. A spherical tumor with diameter of 4 cm corresponds to a volume of 33.5 mL. However, in our experience injecting oropharyngeal tumors or abscesses with lidocaine for anesthetic purposes for biopsy or drainage, respectively, it is typically not feasible to inject more than 10 mL before the injection begins to extravasate from the tissues, likely due to the anatomic constraints of the oropharynx. A total volume of 10 mL is significantly lower than the maximum tolerated dose of 1% lidocaine (31.5 mL for a 70 kg individual). Therefore, tumors will be injected with 1% lidocaine until the injection appears to be evenly distributed into the tumor and begins to extravasate, with a total volume not to exceed 10 mL. The exact volume injected will be recorded for each subject. Notably, the previously referenced breast cancer clinical trial with 1600 patients reported no adverse events related to lidocaine injection.⁶⁶

Biological Correlate for Early Evaluation of Intervention: Pathologic Tumor Response

Advancements in neoadjuvant therapies have led to several systems for evaluating the pathologic treatment response in tumors following surgical removal. Pathological complete response (pCR, eradication of all cancer cells) and major pathologic response (MPR, presence of $\leq 10\%$ viable tumor cells) are commonly used as surrogate clinical markers for predicting long-term survival.⁷⁴⁻⁷⁷ Despite being regarded as the “gold standard” for immunotherapy, pCR and MPR do not fully consider the varying degrees of treatment response within the tumor that may influence clinical outcomes. Therefore, some researchers have also implemented a metric known as the pathological tumor response (pTR) defined as the presence of tumor cell necrosis, keratinous debris, and giant cell/histiocytic reaction, quantified as a percentage of the overall tumor bed (area pathologic response/area pathologic response plus viable tumor).^{78, 79} The calculated pTR rate is scored in increments of 10% and often grouped into pTR-0 ($\leq 10\%$), pTR-1 ($\leq 10-49\%$), and pTR-2 ($\geq 50\%$) to categorize the degree of response. Recent clinical trials in HPV associated OPSCC have successfully used pTR rates as primary endpoints for assessing responses to neoadjuvant pembrolizumab.⁷⁸ pTR scoring will serve as an early metric for evaluating the study intervention.

2 Study Objectives

2.1 Primary Objectives

Determine if intratumoral 1% lidocaine injection at the time of direct laryngoscopy prior to TORS and neck dissection for HPV associated OPSCC is safe and causes a major pathologic treatment effect.

2.2 Secondary Objectives

Determine if intratumoral 1% lidocaine injection at the time of direct laryngoscopy prior to TORS and neck dissection for HPV associated OPSCC improves the locoregional control rates, progression-free survival, metastasis-free survival, and overall survival compared to no injection.

3 Study Design

3.1 General Design

This is a phase I patient-blinded, randomized controlled trial evaluating intratumoral lidocaine injection prior to definitive surgery in HPV associated OPSCC. Patients with OPSCC undergoing direct laryngoscopy who are being considered for definitive TORS

and selective neck dissection, will be eligible. Patients will be randomized and blinded to intratumoral injection of 1% lidocaine (intervention arm) or no injection (control arm) at the time of direct laryngoscopy. After administration of general anesthesia and biopsy, lidocaine will be injected under direct visualization (not exceeding the maximum tolerated dose of 4.5 mg/kg body weight) into the primary tumor. The control arm will receive no injection.

Blood samples will be obtained prior to direct laryngoscopy/study intervention (pre-biopsy) and again after the intervention (post-biopsy). The pTR rate (defined above and in published literature^{78, 79}) will be determined by the designated study pathologist ([name], PhD) with head and neck expertise using increments of 10% for the biopsy and surgery specimens. The scores will be grouped as pTR-0 (<10%), pTR-1 (10%–49%), and pTR-2 (≥50%).

Patients will otherwise receive institutional standard of care treatment including TORS primary site resection, selective neck dissection, and additional indicated adjuvant radiation therapy with or without chemotherapy. All enrolled patients will be assessed for safety measured by adverse events. If a patient does not ultimately receive primary surgery following their direct laryngoscopy/study intervention (based on surgical candidacy, patient preference, or other reasons), then they will not be counted as an evaluable subject, as the primary endpoint pTR requires a surgical specimen for evaluation. If a patient is determined to have a pathology other than HPV associated OPSCC after their direct laryngoscopy, then they will not be counted as an evaluable subject.

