4.3 Patient Selection and Inclusion

OPSCC is now the most common head and neck cancer diagnosed in the United States

with most cases attributed to HPV. HPV associated OPSCC is most frequently seen in middle-aged, white males (not Hispanic or Latino). We expect to have similar eligibility and enrollment demographics as other published trials on HPV associated OPSCC. For reference, RTOG 1016, which compared radiotherapy with cetuximab vs cisplatin, is the largest published randomized trial of HPV associated OPSCC in the United States with the following study demographics:⁸⁰

	IMRT + Cisplatin (n=406)	IMRT + Cetuximab (n=399)	Total (n=805)
Age (years)			
≤ 65	344 (85%)	345 (86%)	689 (86%)
> 65	62 (15%)	54 (14%)	116 (14%)
Mean (standard deviation)	57.7 (8.1)	57.4 (7.8)	57.6 (8.0)
Median (1 st - 3 rd quartile)	58 (52-63)	58 (52-63)	58 (52-63)
Min - max	33 - 83	33 - 80	33 - 83
Gender			
Male	373 (92%)	355 (89%)	728 (90%)
Female	33 (8%)	44 (11%)	77 (10%)
Race			
White	380 (94%)	367 (92%)	747 (93%)
Black or African American	17 (4%)	19 (5%)	36 (4%)
Other	2 (<1%)	8 (2%)	10 (1%)
Unknown	7 (2%)	5 (1%)	12 (1%)
Ethnicity			
Hispanic or Latino	11 (3%)	15 (4%)	26 (3%)
Not Hispanic or Latino	383 (94%)	369 (92%)	752 (93%)
Unknown	12 (3%)	15 (4%)	27 (3%)

4.4 *Subject Recruitment and Screening*

Subjects will be recruited from the practices of Otorhinolaryngology and Radiation Oncology at the University of Pennsylvania. The study CRC will verify eligibility using the criteria outlined in Section 4.1 and 4.2. Patients will be consented either in clinic or in the hospital.

4.5 *Clinical Evaluation and Staging Criteria*

- History and physical examination:
 - Primary tumor extent will be documented by the head and neck surgeon, with a particular focus on the degree (if any) of involvement of the soft palate and/or base of tongue.
- Laboratory studies:
 - HPV status will be determined based on p16-positivity by immunohistochemistry or HPV-positivity by in-situ hybridization.
 - Research blood tests will be drawn 1) prior to direct laryngoscopy/study intervention and 2) after the direct laryngoscopy/study intervention (but before definitive treatment).
- Pathologic evaluation
 - In addition to standard pathologic evaluation of biopsy and surgical

specimens, pTR will be calculated and categorized as pTR-0 ($\leq 10\%$), pTR-1 ($\leq 10-49\%$), and pTR-2 ($\geq 50\%$) by the designated study pathologist ([name], PhD).

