5.1 General study design

Patients will be enrolled to reach 30 evaluable subjects on this phase I patient-blinded, randomized controlled trial investigating the feasibility and safety of intratumoral 1% lidocaine injection at the time of direct laryngoscopy prior to definitive surgery in HPV associated OPSCC patients. Patients with a clinically apparent primary tumor (i.e. clinical T1-T4), any clinical N stage, and M0 disease (per AJCC 8th Edition) undergoing direct laryngoscopy who are being considered for definitive TORS and selective neck dissection, will be eligible. Patients will be blinded to the intervention which will be administered as dictated by the protocol, according to Section 3.1 above. Randomization will be performed using the “Clinical Trial Randomization Tool” from The National Cancer Institute's Division of Cancer Prevention.⁸¹

Clinical evaluations will be performed according to routine clinical care, which is left to the discretion of the treating physician. This will include a baseline evaluation prior to direct laryngoscopy/study intervention.

All patients will be asked to take a short survey about pain (2 questions) at their follow up appointment after their direct laryngoscopy and biopsy.

Locoregional recurrence will be defined as biopsy-proven recurrent squamous cell carcinoma at the original, primary tumor site, or in the neck.

5.2 *Surgery*

Surgery will be performed per standard of care consisting of TORS primary site resection, selective neck dissection, and external carotid artery vessel ligation. The decision to stage the neck dissection and TORS will be determined at the discretion of the head and neck surgeon. Intraoperative continuous monitoring of circulation and respiration will be performed.

5.3 *Radiation Therapy*

Patients who have indications post-operative radiation therapy per NCCN guidelines⁵ will be referred to a radiation oncologist who specializes in the treatment of head and neck cancer within the University of Pennsylvania Health System, with the decision on whether to treat with radiation therapy determined at the discretion of the consulting radiation oncologist.

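### Blinding is stated for the patient only, and the protocol does not say whether the one pathologist who scores the efficacy co-primary (pTR) is masked to arm

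*Protocol*

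**What the plan says.** **Who is blinded.** Each statement on blinding names the patient alone.
- Study Summary, Statistical Methodology: "This is a patient-blinded, randomized phase I study assessing safety, pathologic treatment effects, and oncologic outcomes".
- Section 3.1: "This is a phase I patient-blinded, randomized controlled trial evaluating intratumoral lidocaine injection".
- Section 5.1: "Patients will be blinded to the intervention which will be administered as dictated by the protocol".

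The control arm has no injection and no sham is described, so the operating team knows the arm. Under Dosing Rationale in Section 1, "The exact volume injected will be recorded for each subject".

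**What is scored, and by whom.** Section 1 defines pTR from named histological features, "quantified as a percentage of the overall tumor bed". Section 3.1 gives the scoring to one designated study pathologist "with head and neck expertise using increments of 10% for the biopsy and surgery specimens". Section 4.5 repeats that "pTR will be calculated and categorized as" three groups, with pTR-2 at 50% or more, by the same designated person.

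**How it is used.** Section 6 makes the pTR-2 proportion a co-primary alongside safety and compares the arms by a one-sided Fisher's exact test at 0.05. The alternative is a higher proportion with lidocaine. The planned size is 30 evaluable patients; Section 6 has an equal split, while the Study Summary has them "split approximately equally between the two groups".

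**What is absent.** No section says that the pathologist is masked, that slides are coded for reading, or that a second reader is used. Sections 8.1 and 8.2 put a study number on case report forms and research material and restrict identifiable data. Those rules protect identity and do not conceal allocation.

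**The concern.** A patient cannot influence a histology reading; the pathologist can. The protocol therefore masks the role that matters least for this endpoint and leaves open the role that matters most.

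Whether a specimen counts as pTR-2 can turn on a reading of 40% or 50%, one step on the scale. One person makes that reading. With a one-sided alternative, any tendency to read higher when lidocaine is known to have been given works in the tested direction. Fisher's test takes the counts as given and cannot correct for it.

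Who is masked when an outcome is assessed is a matter of design and conduct. The protocol takes up blinding itself and limits it to the patient, so this is not a detail that can be assumed to sit in a separate analysis plan.

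**Working it through.** The protocol gives no figure for reader error, so there is none to reproduce. Masking the reader changes no design input (sample size, alpha, assumed rates). The check asks how many wrong upgrades the planned test can absorb.

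**Inputs from the protocol.** 30 evaluable patients, taken as 15 v 15; one-sided Fisher's exact test at 0.05; 0% pTR-2 assumed in controls (Section 6). The Study Summary wording also allows splits such as 14 v 16.

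**Inputs assumed.** No true effect, with the same true pTR-2 rate *p* in both arms, and *k* lidocaine specimens wrongly raised to pTR-2, with none raised in controls.

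**Step 1: rejection boundary at 15 v 15.** With no control responders, *a* lidocaine responders give a one-sided p-value of C(15,a)/C(30,a).
- a = 3: 455/4060 = 0.112, not significant.
- a = 4: 1365/27405 = 0.0498, significant.

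With 1, 2 or 3 control responders, the lidocaine arm needs 6 (p = 0.0400), 8 (p = 0.0251) or 9 (p = 0.0302).

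**Step 2: false-positive rate with k upgrades.** Let X and Y be independent Binomial(15, *p*) counts of true responders. Then

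P(reject) = Σ P(X = x) P(Y = y), summed over all (x, y) where x + k lidocaine responders against y control responders give a Fisher p-value of at most 0.05.

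Example, *p* = 5%, k = 2:
- y = 0 needs x ≥ 2: 0.4633 × 0.1710 = 0.0792.
- y = 1 needs x ≥ 4: 0.3658 × 0.0055 = 0.0020.
- Larger y adds a negligible amount. Total 0.0812.

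| Lidocaine v control | True rate, both arms | k = 0 | k = 1 | k = 2 | k = 3 |
|---|---|---|---|---|---|
| 15 v 15 | 5% | 0.3% | 1.7% | 8.1% | 26.2% |
| 15 v 15 | 10% | 1.2% | 4.2% | 11.3% | 23.0% |
| 14 v 16 | 5% | 0.2% | 1.3% | 6.9% | 23.7% |
| 14 v 16 | 10% | 0.9% | 3.3% | 9.4% | 20.9% |
| 16 v 14 | 5% | 0.04% | 0.3% | 2.1% | 9.5% |
| 16 v 14 | 10% | 0.4% | 1.7% | 5.5% | 14.0% |

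**Step 3: the protocol's own control rate, 0%, in both arms.** The result is then fixed by k alone.
- 15 v 15: three upgrades never reach significance; four always do.
- 14 v 16: four are needed (4/14 v 0/16, p = 0.0365).
- 16 v 14: four give p = 0.0664; five are needed (p = 0.0307).

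**Step 4: the same case with a misreading rate.** Suppose the true rate is 0% in both arms and each lidocaine specimen is wrongly read as pTR-2 with probability *q*. The false-positive chance at 15 v 15 is P(Binomial(15, *q*) ≥ 4): 0.5% at *q* = 5%, 5.6% at 10%, 17.7% at 15% and 35.2% at 20%.

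**The case against.** The strongest reply is that this argues from silence. Nothing in the protocol is contradicted, no section shows how the reader would learn the arm, and slide coding may be written in a pathology procedure that is not at hand. It is right that silence does not show an unmasked reader, and no such claim is made here. It does not remove the point, because the protocol states its blinding and confines it to the patient.

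The second reply is that the endpoint has structure: named features, an area ratio, fixed steps, one expert reader for both arms, and a biopsy taken before injection that is also scored. This limits random variation between readers. It does not stop a single reader from leaning one way when the arm is known, and a biopsy score does not mask the reading of the surgical specimen.

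The third reply concerns size, and much of it stands. The misreads are hypothetical, all in one direction, and their probability is unknown. No pTR distribution is given to show that tumours lie near the 50% cut. At low true rates the test is more robust: at 15 v 15, two upgrades give only 0.8% at a true rate of 1% and 2.6% at 2%. The study is also a 30-patient phase I trial that calls itself exploratory, so a positive result would need replication. These points keep the matter at the level of a recommended improvement.

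**Conclusion.** The concern holds. The stated blinding covers the patient only, and the protocol leaves open whether the sole reader of a judged efficacy co-primary knows the arm.

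On the assumptions above, one misread keeps the false-positive rate below 5% in every case tried. At true rates of 5% or 10%, passing 5% takes two or three upgrades in the same direction, depending on the split. From a true 0% in both arms it takes four, or five at 16 v 14. These counts are small against about 15 lidocaine specimens, but how likely they are cannot be judged from the protocol. The change is worth making because the bias is avoidable at little cost and cannot be reliably undone once the only designated reader has scored with knowledge of the arm.

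**What to change.** In Sections 3.1, 4.5 and 5.1, state that the designated pathologist scores pTR on coded surgical-specimen slides without knowledge of allocation or injected volume, and that scores are locked before the arm is revealed. The biopsy slides can be coded in the same way. Keep the patient blinding, and describe the trial as blinded to the patient and to the pTR reader. If masking is already intended, it only needs to be written down.

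The cost is a few protocol sentences and coded slides. No extra reader, patient, procedure or change to the test is needed. The practical burden is keeping allocation and injected volume off the material that reaches the reader, and arranging the order of work if the same person also does the routine clinical reading, which the protocol does not specify.
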